2.8 Summary of Risk and Benefits

The safety profile for ACM (FLAM) has been well-described in the eight clinical studies in patients with AML, and appears to be acceptable for these poor-risk and pretreated patient populations. The early observation of tumor lysis and the potential for renal failure has resulted in an aggressive prophylaxis approach to manage the dramatic lysis of leukemic blasts caused by FLAM. Treatment-related mortality (TRM) for patients treated with alvocidib/FLAM is approximately 8-10%, with a range up to 28% in Study 6 of relapsed/refractory AML patients (particularly among patients over 60 years old). Overall, TRM of alvocidib/FLAM appears to be comparable to other therapeutic options including 7&3 and intermediate- and high-dose cytarabine.

3. STUDY OBJECTIVES

Stage 1: Primary Objective

- To determine the CR rate in patients with relapsed or refractory AML with MCL-1 dependence of $\geq 30\%$

Stage 2: Primary Objective

- To compare CR rates between patients with relapsed or refractory AML with MCL-1 dependence of $\geq 30\%$ receiving 1 cycle of ACM treatment and those receiving 1 cycle of CM.

Exploratory Objective (Stage 2): To determine if treatment with ACM can induce CR in patients with relapsed or refractory AML with MCL-1 dependence of $\geq 30\%$ who failed to achieve CR following 1 cycle of CM.

4. INVESTIGATIONAL PLAN

“FLAM” (alvocidib, cytarabine, mitoxantrone hydrochloride) will now be referred to as “ACM”.

“AM” (cytarabine, mitoxantrone hydrochloride) will now be referred to as “CM”.

4.1 Overall Study Design

This is a Phase 2, open-label, randomized, multicenter, two-stage study to determine if MCL-1 dependence demonstrated by mitochondrial profiling in bone marrow samples will increase the Complete Remission (CR) rate after ACM treatment.

Stage 1 of the study will be single arm (ACM), conducted similarly to the first stage of a Simon 2-stage design. Patients with relapsed or refractory AML with demonstrated MCL-1 dependence of $\geq 30\%$ by mitochondrial profiling in bone marrow will be screened according to study inclusion and exclusion criteria up to 14 days before the initiation of ACM study treatment. Once ≥ 13 patients enrolled in Stage 1 exhibit a CR, CRi, or CRp, enrollment into Stage 1 will close and additional patients will be enrolled in Stage 2 of the study.

Enrollment into Stage 1 will be limited to no more than 23 evaluable patients, however enrollment into Stage 2 may be initiated at any point after confirming CR, CRi or CRp responses in 13 Stage-1 patients.

In Stage 2, patients with relapsed or refractory AML with demonstrated MCL-1 dependence of $\geq 30\%$ by mitochondrial profiling in bone marrow will be randomized 1:1 to receive either ACM or CM. Patients will be screened for study inclusion and exclusion criteria up to 14 days before the initiation of study treatment.

Response assessments in Stage 1 are defined by the International Working Group Criteria [20] and 2010 European LeukemiaNet (ELN) [21]. The 2017 ELN criteria will be used to determine patient responses during Stage 2. Response assessments ([Appendix E](#)) will include:

- CR rate = Percentage of patients achieving CR
- Combined CR Rate = Percentage of patients achieving:
 - CR = Bone marrow blasts $< 5\%$; absence of blasts with Auer rods; absence of extramedullary disease; hematologic recovery (absolute neutrophil count [ANC] $> 1000 \mu\text{L}$ and platelet count $> 100,000 \mu\text{L}$); independence of red cell transfusions; *plus*
 - CRi = Meets all CR criteria except for residual neutropenia (ANC $< 1000 \mu\text{L}$) or lack of recovery of any other hematopoietic cell; *plus*
 - CRp = Meets all CR criteria except for residual thrombocytopenia (platelet count $< 100,000 \mu\text{L}$)[†]

- Combined Response Rate = Percentage of patients achieving:
 - CR
 - CRi
 - CRp †
 - PR = Meets all hematologic values required for CR but with a decrease of at least 50% in the percentage of blasts to $\geq 5\%$ to $\leq 25\%$ in bone marrow
- Overall Survival (OS) = Time from randomization (Day 1) until death from any cause
- Event-free Survival (EFS) = Time from randomization (Day 1) until (a) treatment failure, (b) relapse after CR, or (c) death from any cause, whichever occurs first, censored at 2 years
- Rate of Stem Cell Transplantation = Percentage of patients proceeding directly to stem cell transplantation

†Note that CRp has been retained in definitions for Combined CR Rate and Combined Remission Rate because Stage-1 patients were assessed using the IWG criteria. CRp will not be used for assessing response in Stage-2 patients and, therefore, will not be included in the definitions of Combined CR Rate and Combined Remission Rate in Stage 2.

The CR rate in patients failing 1 cycle of CM and crossing over to receive ACM will also be determined.

Safety assessments will include:

- Mortality from any cause at 30 and 60 days
- Adverse events graded according to National Cancer Institute's Common Terminology Criteria for Adverse Events (NCI CTCAE), version 4.03 in Stage 1 and version 5.0 in Stage 2
 - The multivariate analysis and risk score prediction model by Montesinos and colleagues [22] will be used to assess the potential for development of TLS (*Appendix F*)

Treatment assessments will include:

- Bone marrow biopsies and/or aspirates will be performed at hematologic recovery (ie, absolute neutrophil count (ANC) $> 1000 \mu\text{L}$ and platelet count $> 100,000 \mu\text{L}$) or Day 45, whichever occurs first. Slides from bone marrow will also be collected.
- Complete blood counts and chemistries assessed daily while hospitalized for chemotherapy administration and weekly thereafter

- Overall survival (OS) monitored monthly during year 1, every 2 months during year 2
- Intensive monitoring of renal function, electrolytes and uric acid levels

Pharmacodynamic assessments will include:

- Determination of MCL-1 dependence at prescreening using bone marrow aspirate

Patients who achieve CR, CRi, CRp, or PR after the first cycle (completion of all doses) may receive up to 3 additional optional cycles of treatment.

- After completing the first cycle of treatment, continued use of mitoxantrone is optional.
- Mitoxantrone must be omitted from subsequent cycles if the patient's lifetime daunorubicin equivalent exceeds 460 mg/m² (see [Appendix G](#) for conversion table) or the LVEF drops below 45%.

Patients not demonstrating evidence of CR, CRi, CRp, or PR after the first cycle of treatment will be considered for removal from the study, although with permission of the Medical Monitor, induction treatment may continue, if clinically indicated, and provided there is no evidence of toxicity ≥NCI CTCAE grade 4 (v4.03 in Stage 1, v5.0 in Stage 2; see [Appendix C](#)). This study also includes a crossover option for those randomized to CM (see below).

- Crossover: Patients randomized to CM with progressive disease or no response after 1 cycle of CM may cross over to receive ACM. In addition, patients randomized to CM with the best response of a PR after 2 cycles of CM may also cross over to receive ACM. Patients who cross over to ACM may receive up to a combined total (CM + ACM) of 4 cycles. Patients crossing over who meet the above criteria (lifetime daunorubicin equivalent exceeds 460 mg/m² or the LVEF drops below 45%) will receive only AC (alvocidib and cytarabine) for all cycles instead of ACM.

Complete remission rates will be compared across treatment groups using the Cochran-Mantel-Haenszel general association test stratified by response to most recent induction therapy. The same test will be applied to assess the statistical significance of the secondary response rate endpoints.

Incidence rates of treatment-emergent adverse events (TEAEs) will be summarized within treatment group at the Medical Dictionary for Regulatory Activities (MedDRA) preferred term and primary system organ class levels. Similar summaries will be made for subsets of adverse events (AEs) such as (1) those judged by the Investigator to be related to study treatment, and (2) serious adverse events (SAEs).

Other routine safety assessments (eg, clinical laboratory parameters and vital signs) will be summarized by treatment group using mean, standard deviation, median, minimum and maximum changes from baseline values.

The study is expected to take 20-24 months to enroll up to 137 patients: 25 patients in Stage 1; 56 patients in the 4 Exploratory Arms (closed after Amendment 8); and 56 patients (28 patients in each of two treatment arms) in Stage 2.

4.2 Randomization Criteria

This study follows a randomized, two-stage design. During Stage 1, patients will receive ACM:

- **ACM** – Alvocidib, Cytarabine (ara-c), and Mitoxantrone).

Once a minimum response threshold has been met in Stage 1 as defined in the Statistical Analysis Plan (SAP), Stage 1 will be closed to enrollment and new patients will be enrolled into Stage 2 and randomized 1:1 to receive either ACM or CM:

- **CM** – Cytarabine (ara-c) and Mitoxantrone

Randomization to treatment arm will be stratified by:

- Response to first-line therapy:
 - Refractory: persistent disease or complete remission [CR] duration <90 days
 - Early relapse: CR duration 90 days to 1 year
 - Late relapse: CR duration >1 year but <24 months

4.3 Controls

An active comparator will be used (treatment with cytarabine and mitoxantrone [CM regimen]).

4.4 Patient Population

4.4.1 Number of Patients

A sufficient number of patients with demonstrated MCL-1 dependence by mitochondrial profiling in bone marrow will be screened in order to obtain up to 137 eligible and evaluable patients. This includes 25 patients with MCL-1 dependence $\geq 30\%$ evaluated for response in Stage 1; 56 patients in the 4 Exploratory Arms (closed after Amendment 8); and 56 patients with MCL-1 dependence $\geq 30\%$ (28 patients in each of the two treatment arms) in Stage 2.

Patients who drop out prior to dosing will be replaced, but will still be included in the Intent-to-treat (ITT) analysis population. Patients who drop out of Stage 1 prior to being assessed for response will be replaced, but will still be included in the ITT analysis population and in the Safety analysis population according to the analysis populations defined in *Section 11.3*.

4.4.2 Inclusion Criteria

To be eligible for participation in the study, patients must meet all of the following inclusion criteria:

During Prescreening:

1. Be between the ages of ≥ 18 and ≤ 65 years
2. Have an established, pathologically confirmed diagnoses of AML by World Health Organization (WHO) criteria excluding acute promyelocytic leukemia (APL-M3) with a bone marrow of $>5\%$ blasts based on histology or flow cytometry
3. Be in first relapse (within 24 months of CR) or have failed induction therapy* (no CR or CRi after treatment with an intensive regimen [eg, anthracycline/cytarabine \pm etoposide, gemtuzumab ozogamicin, or cladribine])
*Induction therapy may involve 1 or 2 cycles of the same regimen. Efficacy assessment of induction therapy must be >21 days from the start of the previous induction cycle.
4. Demonstrate MCL-1 dependence of $\geq 30\%$ by mitochondrial profiling in bone marrow

During Screening:

5. Have an Eastern Cooperative Oncology Group (ECOG) performance status (PS) ≤ 2
6. Have a serum creatinine level ≤ 1.8 mg/dL
7. Have an alanine aminotransferase (ALT)/aspartate aminotransferase (AST) level ≤ 5 times upper limit of normal (ULN)
8. Have a total bilirubin level ≤ 2.0 mg/dL (unless secondary to Gilbert syndrome, hemolysis, or leukemia)
9. Have a left ventricular ejection fraction (LVEF) $>45\%$ by echocardiogram (ECHO) or multigated acquisition (MUGA) scan
10. Be nonfertile or agree to use an adequate method of contraception. Sexually active patients and their partners must use an effective method of contraception associated with a low failure rate during and for at least 6 months after completion of study therapy (see *Section 4.7.3*).

11. Be able to comply with the requirements of the entire study.
12. Provide written informed consent prior to any study related procedure. (In the event that the patient is re-screened for study participation or a protocol amendment alters the care of an ongoing patient, a new informed consent form must be signed.)

4.4.3 Exclusion Criteria

Patients meeting any one of these exclusion criteria will be prohibited from participating in this study.

1. Received more than 2 cycles of induction therapy for AML. Investigational agents as part of front-line therapy for AML may be acceptable following discussion with the Medical Monitor. Hydroxyurea is permitted (see #5 below).
2. Received any previous treatment with alvocidib or any other CDK inhibitor
3. Received a hematopoietic stem cell transplant within the previous 2 months
4. Have clinically significant graft versus host disease (GVHD), or GVHD requiring initiation or escalation of treatment within the last 21 days
5. Require concomitant chemotherapy, radiation therapy, or immunotherapy. Hydroxyurea is allowed up to the evening before starting (but not within 12 hours) of starting treatment on either arm.
6. Received >360 mg/m² equivalents of daunorubicin (see *Appendix G* for conversion table)
7. Have a peripheral blast count of $>30,000/\text{mm}^3$ (may use hydroxyurea as in #5 above)
8. Received antileukemic therapy within the last 3 weeks (with the exception of hydroxyurea or if the patient has definite refractory disease). Refractory patients who received therapy within the last 3 weeks may be eligible with prior approval of the Medical Monitor.
9. Diagnosed with acute promyelocytic leukemia (APL, M3)
10. Have active central nervous system (CNS) leukemia
11. Have evidence of uncontrolled disseminated intravascular coagulation
12. Have an active, uncontrolled infection
13. Have other life-threatening illness
14. Have other active malignancies or diagnosed with other malignancies within the last 6 months, except nonmelanoma skin cancer or cervical intraepithelial neoplasia

15. Have mental deficits and/or psychiatric history that may compromise the ability to give written informed consent or to comply with the study protocol.
16. Are pregnant and/or nursing
17. Have received any live vaccine within 14 days prior to first study drug administration

4.5 Study Treatments

4.5.1 Calculation of Dose

The dosage of study drugs will be recalculated at the beginning of each new treatment cycle to reflect changes in the body surface area (BSA) that may have occurred but will remain the same for all treatments within a treatment cycle.

4.5.2 Treatment Plan

This is an open-label, randomized, multicenter, two-stage study in patients with AML with demonstrated MCL-1 dependence of $\geq 30\%$ by mitochondrial profiling in bone marrow who are either in first relapse or have primary refractory AML.

Stage 1 of the study will be single arm and all enrolled in this arm will receive treatment with ACM. Stage 2 will be two-arm; patients enrolled in this stage will be randomized to receive treatment with either ACM or CM.

4.5.3 Treatment Schema

4.5.3.1 Stage 1: Treatment with ACM over Days 1-9

Patients enrolled in Stage 1 will receive treatment with ACM as outlined below:

- **Days 1, 2 and 3: alvocidib (A) - Administer Daily**
30 mg/m² as a 30-minute (± 10 minutes) intravenous (IV) bolus
followed by
60 mg/m² over 4 hours (± 15 minutes) as an IV infusion
- **Days 4 and 5: Rest (no chemotherapy treatment)**
- **Days 6, 7, and 8: cytarabine (C) - Continuous over 72 hours**
2 gm/m² by continuous IV infusion over 72 hours (± 2.5 hours)
(ie, 667 mg/m² daily for total of 2 gm/m²)
- **Day 9: mitoxantrone hydrochloride (M) is administered 12 hours after completion of cytarabine treatment**
40 mg/m² by IV infusion over 1-2 hours (± 10 minutes)

4.5.3.2 Stage 2: Treatment with ACM or CM

Patients enrolled in Stage 2 will be randomized to either ACM or CM and will receive treatment as outlined below:

Stage 2: Randomized to ACM: Treatment with ACM over Days 1-9

Follow the Stage 1 treatment schema above

Stage 2: Randomized to CM: Treatment with CM over Days 1-4

- **Days 1, 2, and 3: cytarabine (C) - Continuous over 72 hours**
2 gm/m² by continuous IV infusion over 72 hours (± 2.5 hours)
(ie, 667 mg/m² daily for total of 2 gm/m²)
- **Day 4: mitoxantrone hydrochloride (M) is administered 12 hours after completion of cytarabine treatment**
40 mg/m² by IV infusion over 1-2 hours (± 10 minutes)

4.5.3.3 Evaluation After Cycle 1

- Patients who achieve CR, CRi, CRp, or PR after the first cycle (completion of all doses) may receive up to 3 additional optional cycles of treatment.
 - After completing the first cycle of treatment, continued use of mitoxantrone is optional.
 - Mitoxantrone must be omitted from subsequent cycles if the patient's lifetime daunorubicin equivalent exceeds 460 mg/m² (see *Appendix G* for conversion table) or the left ventricular ejection fraction (LVEF) drops below 45%.
- Patients not demonstrating evidence of CR, CRi, CRp, or PR after the first cycle of treatment will be considered for removal from the study, although with permission of the Medical Monitor, induction treatment may continue if clinically indicated and provided there is no evidence of toxicity \geq NCI CTCAE grade 4.
- Perform the End of Study Assessments for those patients who do not continue on study to receive at least one additional cycle of treatment (see *Section 5.5*).

4.5.3.4 Crossover (Stage 2)

- Patients randomized to CM with progressive disease or no response after one cycle of CM may cross over to receive ACM.
- Patients randomized to CM with a best response of PR after 2 cycles of CM may also cross over to receive ACM.

- Continued use of mitoxantrone is optional after completion of one cycle of ACM
- Mitoxantrone must be omitted from subsequent cycles if the patient's lifetime daunorubicin equivalent exceeds 460 mg/m² (see *Appendix G* for conversion table) or the left ventricular ejection fraction (LVEF) drops below 45%. Patients crossing over who meet the above criteria will receive only AC (alvocidib and cytarabine) for all cycles instead of ACM.
- Patients who cross over to ACM may receive up to a combined total (CM + ACM) of 4 cycles.

4.6 Management of Toxicities and Dosage Modifications

Suggested doses of supportive care therapies are provided; however, adjustment of the dosages based on the patient's clinical condition or each institution's standard of care is permitted.

4.6.1 Management of Nonhematologic Toxicities

Adverse events may be treated with concomitant medications, as deemed clinically indicated by the Principal Investigator (PI). All concomitant medications must be recorded in the source and on the appropriate case report form (CRF).

Adverse events that are moderate to severe in intensity (see *Section 8.1* and *Appendix C* for toxicity grading) and considered possibly or probably related to study drug treatments may result in the delay or termination of study treatment in affected patients.

4.6.1.1 Hyperkalemia and Tumor Lysis Syndrome

Tumor lysis may occur as part of initial cytoreductive therapy. The most extreme form, known as Tumor Lysis Syndrome (TLS), is characterized by hyperkalemia, hyperuricemia, hyperphosphatemia, increased lactate dehydrogenase (LDH), coagulopathy, and a potential cytokine release syndrome.

Mandatory IV hydration with 0.45% NaCl (or similar hydration fluid per institutional standard) sterile solution at 100 cc/hour for at least 10 hours prior to initiation of the first dose of chemotherapy during Cycle 1 (optional for subsequent cycles) in all treatment arms. If, by Day 4, there is no evidence of tumor lysis syndrome, the hydration rate can be reduced to a maintenance level.

Diligent monitoring of urine output **frequently** to ensure that fluid output equals fluid input. If input is greater than output by 10%, administration of diuretics is encouraged. **Replacement of excessive fluid losses, including from diarrhea, should be done unless otherwise clinically indicated.**

- Mandatory allopurinol orally each day of dosing for first cycle to be started at same time as initiation of IV hydration in all treatment arms.

- Mandatory oral phosphate binder to be started at the same time as initiation of IV hydration in all treatment arms, unless contraindicated.
- Evaluation of laboratory indicators of tumor lysis syndrome (TLS)
 - Tumor lysis laboratory evaluations ('tumor lysis labs') include electrolytes (sodium, potassium, chloride, and carbon dioxide) as well as creatinine, calcium, lactate dehydrogenase (LDH), uric acid, and phosphorus levels.
 - For patients **at high risk** for TLS including those with risk scores of ≥ 2 according to the table in *Appendix F*, those with monocytic leukemia phenotype, or those with a history of FLT3 positive AML:
 - Patients randomized to ACM (or who cross over to ACM after failure of CM):
 - Obtain a STAT serum potassium at end of alvocidib infusion
 - Strongly recommend serum potassium at 2 hours post end of alvocidib infusion as best practice
 - Obtain full TLS panel at 4 hours post end of alvocidib infusion
 - If evidence of clinically meaningful TLS, obtain TLS panel every 2 hours during the first 24 hours post end of alvocidib infusion (LDH levels are recommended to be assessed at least once every 24 hours).
 - If no evidence of clinically meaningful TLS, obtain TLS panel every 4 hours during the first 24 hours post end of alvocidib infusion (LDH levels are recommended to be assessed at least once every 24 hours).
 - If, after the first 24 hours post end of alvocidib infusion, there is no evidence of TLS, obtain TLS panel approximately every 6 hours for the remainder of alvocidib treatment and then every 12 hours after completion of alvocidib and during cytarabine and mitoxantrone (LDH levels are recommended to be assessed at least once every 24 hours).
 - Monitor fibrinogen levels at baseline and then as clinically indicated.
 - Patients who are determined to be at intermediate- or high-risk for TLS should be considered for rasburicase prophylaxis according to institutional standards

- *Patients randomized to CM:*
 - During the first 24 hours - Monitor tumor lysis labs at the start of cytarabine and approximately every 6 hours. Laboratory studies during this period should be run as a “STAT” to ensure the results are available in a timely manner.
 - If no evidence of TLS during the first 24 hours, then monitor tumor lysis labs every 12 hours until completion of mitoxantrone.
 - Monitor fibrinogen levels at baseline and then as clinically indicated.
- For patients **NOT at high** risk for TLS:
 - *Patients randomized to ACM (or who cross over to ACM after failure of CM):*
 - During the first 24 hours - Monitor tumor lysis labs at the start of alvocidib and approximately every 4 hours. Laboratory studies during this period should be run as a “STAT” to ensure the results are available in a timely manner (LDH levels are recommended to be assessed at least once every 24 hours).
 - If no evidence of TLS during first 24 hours, then monitor tumor lysis labs approximately every 6 hours for the remainder of alvocidib treatment and then every 12 hours after the completion of alvocidib and during cytarabine and mitoxantrone (LDH levels are recommended to be assessed at least once every 24 hours).
 - Monitor fibrinogen levels at baseline and then as clinically indicated.
 - *Patients randomized to CM:*
 - During the first 24 hours - Monitor tumor lysis labs at the start of cytarabine and approximately every 6 hours. Laboratory studies during this period should be run as a “STAT” to ensure the results are available in a timely manner.

- If no evidence of TLS during first 24 hours, then monitor tumor lysis labs every 12 hours until completion of mitoxantrone.
- Monitor fibrinogen levels at baseline and then as clinically indicated.

Risk of TLS and Guidelines for Management of High Risk Patients

TLS management during treatment with alvocidib was implemented in previous studies, which included medical prophylaxis for hyperuricemia, as well as aggressive monitoring and management of hyperkalemia and other biochemical laboratory abnormalities. Rapid development of hyperkalemia has been of particular concern in earlier studies. While these guidelines are not necessarily consistent with specific standard recommendations for the treatment of TLS, they are recommended based on previous experience with the treatment of patients with alvocidib. These measures resulted in a lower incidence of TLS without adverse outcomes.

For this reason, you are encouraged to follow the recommended guidelines below but may follow your own institution's protocols in determining the best treatment for your patients.

- If potassium levels are increasing to >4.0 mEq/L, patients should receive a 30-gm dose of sodium polystyrene sulfonate, unless there are other likely causes of hyperkalemia other than TLS or contraindication to its use.
- If potassium levels rise to >5.0 mEq/L, in addition to the 30-gm dose of sodium polystyrene sulfonate, patients should also receive 10 units of IV rapid-acting insulin and 25 gm (one ampule) of IV dextrose 50%, unless there are other likely causes of hyperkalemia other than TLS or contraindication to its use.
- If potassium levels rise to >5.5 mEq/L, patients should be considered for emergent intermittent or continuous dialysis.
- Calcium supplementation should only be given for symptomatic hypocalcemia in this setting to avoid renal precipitation of calcium phosphate crystals.
- Patients who develop clinical evidence of cytokine release syndrome or who have hyperkalemia requiring dialysis will receive immediate steroid therapy with an equivalent of at least 20 mg of IV dexamethasone.

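### Patients who cross over from CM get their first alvocidib in Cycle 2 or 3, where hydration and allopurinol are no longer required; the requirement should follow the first alvocidib cycle

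*Protocol*

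**What the plan says.** Section 4.6.1.1 sets three preventive measures against tumor lysis syndrome (TLS).

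- Hydration at 100 cc/hour for at least 10 hours is required "prior to initiation of the first dose of chemotherapy during Cycle 1 (optional for subsequent cycles) in all treatment arms".
- Allopurinol: "Mandatory allopurinol orally each day of dosing for first cycle to be started at same time as initiation of IV hydration".
- Phosphate binder: "Mandatory oral phosphate binder to be started at the same time as initiation of IV hydration in all treatment arms, unless contraindicated". No cycle is named.

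The Study Summary makes all three required in Cycle 1 and optional later. In Stage 2, Section 5.4.1.1 applies them to every patient before the first Cycle 1 dose, in both arms. For Cycles 2 to 4, Section 5.4.5.1 and Appendix A (Stage 2, Cycles 2-4, notes k, l and m) make each one conditional on clinical indication.

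Section 4.5.3.4 lets CM patients cross over after one CM cycle (progressive disease or no response) or after two (best response PR), with CM and ACM cycles counted together to a maximum of four. For laboratory monitoring, Section 4.6.1.1 puts patients "or who cross over to ACM after failure of CM" on the ACM schedule in both TLS risk groups.

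**The concern.** The preventive requirement is tied to the study cycle number, whereas the hazard the protocol describes is tied to the drug. Section 2.8 explains that early tumor lysis and possible renal failure led to an "aggressive prophylaxis approach to manage the dramatic lysis of leukemic blasts caused by FLAM", the regimen now called ACM. Section 4.6.1.1 adds: "Rapid development of hyperkalemia has been of particular concern in earlier studies".

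A crossover patient meets that regimen for the first time after the requirement has lapsed. The same patient had to receive hydration and allopurinol before CM, which contains no alvocidib, but need not receive them before alvocidib. What is at stake is a preventable and occasionally fatal toxicity in a subgroup that the design creates on purpose.

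**Working it through.** The plan states no figure on this point, so the check sets the texts side by side.

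**Step 1: where each measure is required.**

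| Place in the Protocol | Hydration | Allopurinol | Phosphate binder |
|---|---|---|---|
| Section 4.6.1.1 | Cycle 1; later optional | First cycle | Required, no cycle limit |
| Study Summary, Study Treatment | Cycle 1; later optional | Cycle 1; later optional | Cycle 1; later optional |
| Section 5.4.1.1 (Stage 2, Cycle 1) | All patients | All patients | All patients |
| Section 5.4.5.1 (Stage 2, Cycles 2-4) | If indicated | If indicated | If indicated |
| Appendix A, Stage 2, Cycles 2-4, notes k-m | If indicated | If indicated | If indicated |

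For hydration and allopurinol every row agrees: nothing is required after Cycle 1. For the binder, the first row differs from the rest.

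**Step 2: the cycle of first alvocidib after crossover (Section 4.5.3.4).**

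- Progressive disease or no response: 1 CM cycle + 1 = Cycle 2.
- Best response PR: 2 CM cycles + 1 = Cycle 3.

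Section 5.4.5 and note a of the Appendix A schedule both place crossover inside Cycles 2 to 4.

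**Step 3: could Cycle 1 mean the first alvocidib cycle?** The Protocol counts CM and ACM cycles together, and nothing restarts the numbering at crossover. The SAP (Section 3) starts Cycle 1 at the first dose of study drug and includes cytarabine and mitoxantrone in study drug. That SAP was written against Amendment 7, but it is the only explicit definition in the documents.

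**Step 4: who is affected.** Stage 1 patients and Stage 2 ACM patients receive their first alvocidib in Cycle 1, with the measures required. Exclusion criterion 2 (Section 4.4.3) bars prior alvocidib, so every crossover patient is naive to it. Crossover patients are the only group in these two stages that starts alvocidib without the requirement.

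**Step 5: laboratory monitoring.** Section 4.6.1.1 covers crossover patients. Two other places lag behind it: the Study Summary limits TLS laboratory evaluation to Cycle 1, and Sections 5.4.5.3 and 5.4.5.4 list tumor lysis labs without pointing to the alvocidib-timed schedule.

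**Step 6: is the hazard real in pretreated patients?** Table 4 gives TLS in 15/47 (32%) in Study 2, with one patient needing dialysis; 47 equals its 24 relapsed plus 23 refractory patients (Table 2). In Study 3, one AML patient needed dialysis and one death was TLS followed by fungal sepsis. Study 2 used bolus dosing and Study 3 was monotherapy, so these figures show that the hazard exists and say nothing about its rate here.

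**Step 7: size.** The documents give no crossover uptake and no TLS rate without required prophylaxis. The 9% cited for the hybrid regimen (Section 2.7) comes from earlier studies, and Section 4.6.1.1 says TLS management, including medical prophylaxis, was in place in earlier alvocidib studies. No estimate of excess cases follows.

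**The case against.** The strongest reply is that the rule is a coherent choice. Section 4.6.1.1 opens with "Tumor lysis may occur as part of initial cytoreductive therapy", and the Cycle 1 requirement covers the CM arm as well. On that view TLS belongs to the first cytoreduction on study, which crossover patients have already had. The investigator may still give prophylaxis, the alvocidib-timed labs and potassium thresholds apply, and patients at intermediate or high risk "should be considered for rasburicase prophylaxis according to institutional standards".

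Most of this stands, and it lowers the severity. It does not close the gap. Every Stage 2 patient has already had induction therapy before entry, yet prophylaxis is still required in Cycle 1. The first crossover route admits progressive disease or no response, where a reduced leukemic burden cannot be assumed. Labs detect lysis but do not prevent it, and ten hours of pre-hydration cannot be supplied once potassium is rising.

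Two further objections also hold. Section 2.8 does not name the three measures, and the hyperkalemia passage credits medical prophylaxis for hyperuricemia, which supports allopurinol more directly than hydration or the binder. And a blanket hydration requirement could do harm: crossover patients who receive AC include those whose LVEF has fallen below 45% (Sections 4.1 and 4.5.3.4). The fix has to allow for them.

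The binder discrepancy is probably a missing phrase, because the bullet ties the binder to the start of hydration, which is itself limited to Cycle 1.

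**Conclusion.** The point holds as a textual gap. For hydration and allopurinol, no sentence extends the requirement to the first alvocidib cycle after crossover, and confidence in that reading is high. The binder inconsistency is secondary. It is worth fixing because the change is cheap and the protocol already recognizes the same risk in its laboratory schedule.

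Three stronger readings are not supported:

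- A reader might infer that crossover patients are unprotected. They are monitored on the ACM schedule, and prophylaxis is permitted.
- A reader might multiply the expected number of CM patients without CR by a published TLS rate. Lacking CR is not the crossover criterion (CRi, for example, does not qualify), uptake is unknown, and the cited rates come from other schedules or from studies that used prophylaxis.
- A reader might infer an effect on the trial's inference. The primary endpoint is CR after Cycle 1, before any crossover, so alpha and power are unchanged.

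It would equally be too strong to say that laboratory monitoring is fully settled, given the Cycle 1 limit in the Study Summary.

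**What to change.** State the following in Sections 4.5.3.4, 4.6.1.1 and 5.4.5.1, the Study Summary, and Appendix A (Stage 2, Cycles 2-4, notes k, l and m):

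> IV hydration for at least 10 hours before dosing, allopurinol on each dosing day and an oral phosphate binder are mandatory, unless contraindicated, in Cycle 1 in both arms and in each patient's first alvocidib-containing cycle, including the first ACM or AC cycle after crossover; they are optional in other cycles. In crossover patients with LVEF below 45% or at risk of fluid overload, the investigator may reduce or omit the hydration volume, with the reason documented; allopurinol and the TLS laboratory schedule still apply.

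This also settles the binder text. In the Study Summary, extend the Cycle 1 limit on TLS labs to the first alvocidib cycle after crossover, to match Section 4.6.1.1.

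The cost is one further prophylaxis period per crossover patient. At 100 cc/hour, ten hours is 10 x 100 = 1,000 cc before dosing. If that rate is kept until the Day 4 review, it adds 24 x 100 = 2,400 cc per day, which is why the exemption is needed. The change requires a protocol amendment with IRB/IEC approval before use (Section 12). It adds no new type of procedure and leaves the sample size and analysis as they are.
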